Initial assessments will be conducted in the few weeks preceding patients' already-scheduled appointments for dental treatment at TUKSoD. Patients meeting inclusion and exclusion criteria will then be offered I-CBT or the control intervention, to occur immediately prior to their scheduled dental treatment appointment. Efficacy based on primary outcome measures (e.g., reduction from baseline on self-rated and clinician-rated measures of dental anxiety/fear) and secondary outcome measures will be examined at assessments one and three months thereafter. Some additional interview ratings will be gathered from patients after they complete the dental anxiety intervention and after they complete the pursuant dental treatment appointment, and one brief questionnaire will be administered six and twelve months later. Finally, we will examine the impact that the intervention may have on attendance at scheduled dental appointments over the next 12 months.

2) Protocol Title

Efficacy of an Internet-based intervention for dental anxiety

3) Investigators

Page 1 of 28 Revision: May 12, 2023

[name], Associate Professor, Chair, and Residency Director, Pediatric Dentistry and Community Oral Health Sciences, Maurice H. Kornberg School of Dentistry, Temple University

[name], Assistant Professor, Department of Oral Health Sciences, Maurice H. Kornberg School of Dentistry, Temple University

4) Objectives

The primary goal of human subjects activities described in this protocol is to evaluate the efficacy of the Internet-based intervention for dental anxiety among patients presenting to the participating clinic(s). To achieve this overall goal, we propose 3 primary objectives:

Objective 1: We will compare the efficacy of I-CBT as administered by personnel with training and experience in CBT to the efficacy of the intervention as administered by dental assistants who have undergone a brief but specific training in the administration of the intervention, a goal which would allow the greater dissemination of this intervention. We will also examine within-group reduction of anxiety at assessments one and three months after the administration of the intervention.

Objective 2: We will compare the efficacy of the intervention, administered either by CBT personnel or dental staff, to an active control condition, the viewing of the control video and the notification of the dental provider of the patient's score on a measure of dental anxiety before the dental appointment.

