basic training in the nature and use of cognitive coping skills. (3) The third video was filmed from the perspective of a patient in the dental chair and provides additional and more intensive exposure to the feared dental procedure. The voiceover is a "dialogue" between the acting patient in the video, who presents cognitive coping from a self-administered/self-help perspective, and the participating patient, who is led through the steps to develop coping thoughts to counter his/her own anxious thoughts. The intervention closes with a brief module providing additional motivational enhancement for attending future dental appointments. Upon completing the intervention, patients attend their scheduled dental appointment and are encouraged to use the skills they learned from the intervention to cope with any anxiety they experience during that appointment.

The computer-based intervention was piloted on a sample of six dental patients from the TUKSoD Clinics (Potter et al., 2016). All patients completed the experimental intervention and attended their appointment for dental care, and 5/6 were contacted and re-assessed after one month. Three patients demonstrated clinically significant reductions in dental anxiety, and the remainder demonstrated lesser improvements. We next conducted a randomized controlled trial of the experimental intervention in comparison to a waitlist control condition (N = 151; Tellez et al., 2015). The computer-based intervention resulted in greater declines in dental anxiety, and clinician ratings of dental fear and avoidance were also markedly reduced. Among those who met criteria for dental phobia at baseline, a larger percentage of treated patients no longer did so after the treatment interval than was the case for patients assigned to the waitlist condition. Patients who received this computerized dental anxiety intervention reported high levels of satisfaction (83% were "very satisfied").

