A post-baccalaureate study coordinator with a background in psychology or a related field will perform many important tasks for the U01 project. After appropriate training, the study coordinator will conduct the bulk of the initial telephone screening interviews. He/she will also conduct diagnostic interviews at baseline and one-month and three-month follow-up assessments and track attendance at scheduled dental appointments for the 12-month period following the dental anxiety intervention. He/she will also complete reliability ratings for diagnostic interviews conducted by other study staff, providing full coverage of this activity with the graduate student. The study coordinator will also be charged with the rating of treatment fidelity/adherence of a portion of the

Page 6 of 28 Revision: May 12, 2023

interventions completed during the U01 project. The study coordinator will also conduct a range of data entry and management activities.

The dental staff for the proposed U01 will be two or more part-time dental assistants or expanded function dental assistants as defined in the State of Pennsylvania working with [name] at TUKSoD (one full-time equivalent). They will be trained in the administration of the Internet-based dental anxiety intervention by a psychologist, postdoctoral fellow, or doctoral student highly trained in CBT and the specific online intervention, and they will administer the dental anxiety intervention to those patients randomly assigned to the arm of the trial in which the intervention is delivered by dental staff. They will also assist in the payment of study subjects and other day-to-day tasks when these activities cannot be performed by the post-baccalaureate study coordinator.

7) Prior Approvals

See attached letters of support from the Directors of the Faculty Practice Clinic and the Graduate Clinics of TUKSoD.

8) Study Design

a) Recruitment Methods

Approximately 550 patients will participate in this research, roughly evenly divided between the three arms of the study.

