Time 5 is the follow-up contact three months (12-15 weeks) after the day of the dental anxiety intervention and the scheduled dental appointment. The full list of assessments administered at the pre-intervention assessment session will be re-administered. This includes the ADIS-5 interview, amended to include some debriefing questions as described above, and all questionnaires including the CSQ-8. This session will be scheduled as an in-person visit, with both interview and questionnaires completed in the research offices. However, if logistical barriers or scheduling difficulties arise, the session may be conducted by telephone. In that circumstance, questionnaires may be administered over the phone or online. This assessment is identical to the one at Time 4. Brief (5-item) assessments will also be conducted by phone or online at 6- and 12-month follow-ups. Attendance at dental appointments will continue to be monitored until 12 months have passed since the day of the dental anxiety intervention.

Study Procedures/Evaluations

A table is provided below which lists the measures to be administered and the timing of their administration:

Table 1. Measures and Timing of Their Administration

Measure	Initial	Baseline	Dental	1-mo	3-mo	6-mo	12-mo
	Screen	Assess-	Anxiety	Follow-	Follow-	Follow-	Follow-
		ment	Intervention/	up	up	up	up
			Index Dental				
			Appointment				
Modified Dental Anxiety Scale	X	X		Χ	Χ	Χ	Χ
Medical Screening Interview	X						
Anxiety and Related Disorders		X		X	Χ		
Interview Schedule-5 Specific Phobia							
Module							
Post-Dental Anxiety Intervention			X				
Debriefing Interview							
Post-Dental Appointment Debriefing			X				
Interview							
Pain Intensity Numeric Rating Scale			Х				
Pain Sensitivity Index		Х		Х	Х		
Anxiety Sensitivity Index-3		Х		Х	Х		
Distress Tolerance Scale		Х		Х	Х		
Fear Questionnaire Blood-Injury-		Х		Х	Х		
Injection Subscale							
PROMIS-Sleep Disturbance-Short	_	Х		Х	Х		
Form							

Page 11 of 28 Revision: May 12, 2023

PROMIS-Sleep-Related Impairment-	Х		Х	Х	
Short Form					
Sheehan Disability Scale	Х		Х	Х	
Client Satisfaction Questionnaire-8		Χ	Х	Х	

Initial Screening Measures

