Pain Intensity Numeric Rating Scale (PI-NRS). The PI-NRS is a widely utilized 11-point measure that assesses physical pain intensity on a scale ranging from 0 (no pain) to 10 (worst possible pain). The PI-NRS has been used to assess pain intensity in several studies conducted in medical settings (Farrar et al., 2001, 2010; Rowbotham et al., 2004; van der Roer, 2006). Anxiety increases subjective pain experience, and therefore this scale will be used to assess the intensity of dental related pain that participants experienced during their scheduled dental appointment and expect to experience at their next dental appointment. The PI-NRS will be administered as part of the post-dental-appointment debriefing interview.

Attendance at Dental Appointments

Given that avoidance of dental appointments is strongly connected to dental anxiety, we will also assess whether the Internet-based dental anxiety intervention increases attendance at future dental appointments. We will utilize TUKSoD's automated scheduling system (axiUm, http://www.axiumdental.com/) to do so. It is acknowledged that attendance may be influenced by factors unrelated to dental anxiety, but it is a reasonable hypothesis that anxious avoidance plays a role in attendance, and individuals with dental phobia are less likely to visit a dentist at least once a year than persons without. Thus, it is of interest to determine whether attendance at appointments scheduled prospectively after the index appointment is affected by treatment, and we will monitor this for the following 12-month interval. These data will not be collected for active control patients, who will be offered the intervention to be administered before their first scheduled dental appointment after the completion of the 3-month follow-up.

Planned Analyses

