injury-injection phobia). Statistical significance will be set at p < .05. MI will be used to handle missing follow-up data as described below.

Specific Aim 3

Aim 3 examines the impact of the intervention on attendance at scheduled dental appointments over the following 12-month period to determine whether the intervention affects avoidance of dental procedures. First, we will examine whether the overall attendance rate is changed from pre- to post-intervention using a one-sample Chisquare test comparing the 12-month periods immediately before and immediately after the delivery of the intervention. The two intervention groups combined will be used for this analysis. We will also use a Chi-square test to compare post-intervention attendance rates between the two intervention groups. We expect the attendance rates will be similar for the two groups. Finally, we will conduct logistic regression analyses predicting attendance/nonattendance among intervention patients who did or did not demonstrate reduction in dental anxiety at 3-month follow-up. Relevant demographic characteristics and other potential confounding variables or moderators will be included in the final logistic models.

Missing Data

MI will be used to handle missing follow-up data when conducting ITT analysis for Specific Aims 1 and 2. There will be three steps in the MI procedure: 1) The missing follow-up data will be filled in 100 times to generate 100 complete datasets; 2) The 100 datasets will be analyzed by analyses of covariance with follow up scores at 1-month or 3-month as outcomes and treatment groups as the independent variable (Tr1 vs. Tr2 for Specific Aim 1, or Tr1 + Tr2 vs. AC for Specific Aim 2), controlling for baseline scores; 3) The results from the 100 complete datasets will be combined for the MI inference (Rubin 1987). SAS PROC MI and PROC MIANALYZE will be used for multiple imputation analysis using SAS 9.4 (SAS Institute Inc., Cary, NC, USA).

Analysis of Secondary Objectives

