individualized treatment as needed. During this time, to the extent that clinical circumstances allow, he/she will attempt to ascertain whether specific portions of the intervention contributed to the patient's distress (that is, to the extent possible, he/she will attempt to conduct the post-intervention debriefing interview or gather as much of that type of information as the patient will tolerate). [name] or [name] will be available by cell phone to consult as needed in this process.

For the second reason (failure to attend the following dental appointment), the patient will be withdrawn from study consideration unless the dental appointment can be rescheduled within 72 hours. We will attempt to help patients do so, because it is likely that they would still benefit from the dental anxiety intervention if the dental appointment can be rescheduled more or less immediately; research staff will interact with dental clinic staff to facilitate this as much as possible.

For the third reason (failure to attend the dental anxiety intervention), the patient will be withdrawn after reasonable attempts to reschedule have failed or if there is a rescheduled appointment and the patient fails to appear.

For the fourth reason (failure to complete assessments), the circumstances will be different depending on the timing of the problematic assessment. If the patient does not complete the pre-intervention assessments, the intervention will not be delivered, and thus the patient will be effectively withdrawn. The patient will be called no less than 3 times to facilitate such completion, but a number of patients may not complete because of this issue. They will be replaced so that we reach our enrollment target. If the patient fails to complete assessments at follow-up, no less than 3 calls will be made, but the patient will be considered lost to follow-up rather than withdrawn. In our recent randomized trial (Tellez et al., 2015), which included only a one-month follow-up, only 2 of 46 intervention patients were lost to follow-up in this way.

e) Privacy & Confidentiality

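### The attendance definition and the Aim 3 analysis rule use different windows; read literally, the analysis rule takes in the index visit, which would push the post-intervention attendance rate up with no treatment effect

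*Combined protocol and SAP*

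**What the plan says.** Two parts of the protocol define the Aim 3 window, and they differ.

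- Section 8(c), Attendance at Dental Appointments, states the interest as being to "determine whether attendance at appointments scheduled prospectively after the index appointment is affected by treatment", monitored over the following 12 months. The index visit is outside this definition. The same section says attendance is not collected for active controls.
- Planned Analyses, Specific Aim 3, specifies a one-sample chi-square test "comparing the 12-month periods immediately before and immediately after the delivery of the intervention", with the two I-CBT arms pooled. It neither repeats the restriction to later appointments nor refers to it.

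On timing, the Abstract says the intervention or control session is "to occur immediately prior to their scheduled dental treatment appointment", and section 5 says "Upon completing the intervention, patients attend their scheduled dental appointment". Two other places start the clock at the intervention. In section 6 the coordinator is to "track attendance at scheduled dental appointments for the 12-month period following the dental anxiety intervention". Under Follow-up Visits (Times 4 and 5), "Attendance at dental appointments will continue to be monitored until 12 months have passed since the day of the dental anxiety intervention".

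On who remains, section 8(d) says that if the dental appointment after the session is missed, "the patient will be withdrawn from study consideration unless the dental appointment can be rescheduled within 72 hours". For a missed I-CBT session, "the patient will be withdrawn after reasonable attempts to reschedule have failed" or a rebooked session is also missed.

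**The concern.** Attendance is the third of three primary objectives, although Planned Analyses names only the MDAS and the ADIS-5 fear rating as primary outcomes. With no attendance data from controls, the pre-post contrast is the only planned test of whether attendance changed after I-CBT, and no concurrent arm would expose an artefact in it.

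A programmer working from the Specific Aim 3 text alone would take the index visit as the first appointment of the post-period. Retention in the study largely settles whether that visit was kept, and the pre-period has no matching visit. The comparison would then lean towards improvement whatever I-CBT did. The same visit, added to both I-CBT arms, would draw their rates together in the chi-square test where the plan expects similarity.

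**Working it through.** The plan gives no attendance rate, visit count or power figure for Aim 3, so there is no stated result to reproduce.

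**Inputs.** From the documents: about 550 patients in three roughly equal arms, so 550 × 2/3 = 367 in the I-CBT arms. Assumed: 20% not analysed, leaving 293; p, the attendance rate per appointment, equal in both periods (no effect); k, the number of later appointments per patient; two-sided 0.05 (the plan states 0.05 for Aims 1 and 2 only); independent appointments.

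**Size of the rise.** If every analysed patient kept the index visit, the post-period rate is (1 + kp)/(k + 1). Subtracting p gives (1 - p)/(k + 1). For example, p = 0.8 and k = 4 give 0.2/5 = 4.0 points.

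**False-positive rate.** The post-period count is N + Binomial(Nk, p) out of N(k + 1), tested against p by the one-sample chi-square, with p taken as known and N = 293:

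| k | Rise in points at p = 70%, 80%, 90% | False-positive rate at p = 70%, 80%, 90% |
|---|---|---|
| 2 | 10.0, 6.7, 3.3 | 1.00, 1.00, 0.95 |
| 4 | 6.0, 4.0, 2.0 | 1.00, 0.98, 0.73 |
| 6 | 4.3, 2.9, 1.4 | 0.99, 0.91, 0.59 |

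If both rates are estimated and compared by a pooled two-proportion test, the figures are 0.99, 0.92, 0.63 at k = 2 and 0.94, 0.76, 0.43 at k = 4.

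**Less than full index attendance.** If a share a of analysed patients kept the index visit, the rise is (a - p)/(k + 1), which is zero at a = p. At k = 3 and a = 0.95 it is 6.3, 3.8 and 1.3 points for p = 0.7, 0.8 and 0.9. If instead a share f missed, rebooked within 72 hours and had the miss counted, the rise is (1 + kp)/(1 + f + k) - p. At k = 3 and f = 0.05 it is 6.5, 4.0 and 1.4 points.

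False-positive rates under the same one-sample test, N = 293, for k = 2, 4, 6:

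- p = 0.9, 5% rebooked with the miss counted: 0.43, 0.28, 0.20
- p = 0.9, 95% index attendance: 0.37, 0.22, 0.18
- p = 0.9, 90% index attendance: nominal
- p = 0.8, 90% index attendance: 0.71, 0.47, 0.36
- p = 0.7, any of these cases: 0.81 or more

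**Index visit excluded.** The expected change is zero. A check with between-patient variation (mean rate 0.7, k = 2, intraclass correlation 0.2, index missers withdrawn) gave 0.761 before and 0.761 after with the index visit left out, and 0.841 after with it counted.

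**Error rate after exclusion.** With p truly known, the one-sample test rejects 4.8% to 5.3% of the time. But the pre-period rate is itself observed. With equal visit numbers in the two periods, its sampling error doubles the variance of the difference, so the real rejection rate is 2[1 - Φ(1.96/√2)] = 2[1 - Φ(1.386)], about 0.166. Simulation gives 16-17% for k = 2, 4, 6 and p = 0.7 to 0.9.

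**Arm comparison.** A true difference d between the I-CBT arms becomes dk/(k + 1) when both arms carry the same always-kept visit: a loss of 33% at k = 2 and 20% at k = 4.

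**The case against.** The best reply is that the attendance section already defines the outcome and the Specific Aim 3 text only names a test and two periods. Read together, the index visit, booked before enrolment, is out. Section 8(d) also calls the dental appointment integral to the intervention, so the period after delivery could mean after that visit. The passages that start the clock at the intervention describe monitoring and do not say which visits are scored. This is a fair reading and probably the intended one. It does not close the point: Intermediate Visits (Times 2 and 3) treats the end of the intervention and the end of the following appointment as separate events, and the analysis text carries no exclusion.

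A reader might infer that every patient in Aim 3 attended the index visit by rule. The documents do not go that far. Planned Analyses promises both per-protocol and intention-to-treat analyses, and no Aim 3 analysis set is given. Restricting multiple imputation to Aims 1 and 2 does not rule out an intention-to-treat set for Aim 3, since attendance comes from the scheduling system and may need no imputation. A retained patient may also carry a missed visit that was rebooked. Both cases reduce the bias, sharply so when p is near 90%.

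The unit of the rate is also undefined. Scored as keeping at least one visit, retained patients would be 100% attenders in the post-period, and a logistic model of that outcome would have no non-attenders among them. Scored as keeping every visit, an attended index visit changes nothing for patients with a later appointment.

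**Conclusion.** The two windows conflict, and the literal Specific Aim 3 window would bias the pre-post comparison upward under an attended/scheduled rate. The bias is at most (1-p)/(k+1) and is zero when index attendance is no higher than the pre-period rate. It is large for p around 70% in every case examined. At p around 90% it ranges from substantial to nil, depending on how index misses are handled. These sizes rest on assumed p and k and on independent visits.

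Two stronger readings are not supported. One is that the trial will report a spurious improvement: the attendance section already excludes the index visit, and an analyst following it would avoid the bias. The other is that aligning the windows restores a 5% error rate: it removes the index-visit bias, but the one-sample test still rejects about 16-17% of the time if the observed pre-period rate is treated as fixed.

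The window should be corrected. It bears on a primary objective and costs almost nothing to settle.

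**What to change.** Add to Specific Aim 3: the index appointment, and any replacement within 72 hours, counts in neither period; post-intervention appointments are those after it, up to 12 months from the intervention. Apply this to the pre-post test, the comparison of the two I-CBT arms and the logistic model.

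Replace the one-sample test with a comparison that treats both periods as estimated in the same patients, for example a paired or patient-clustered analysis. State whether the rate is per appointment or per patient, name the Aim 3 analysis set, and report by arm how many received I-CBT and then left under the 72-hour rule.

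The scheduling system already holds the appointment records, so no new data are needed. The downside is that patients with no later appointment have no per-appointment rate, so the plan must say how they are handled. The protocol revision is dated May 12, 2023 and completion was hoped for by July 31, 2023. The change should be made before Aim 3 results are seen; if they have been seen, report both windows.

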Objective 3: We will examine the impact that the intervention has on attendance at scheduled dental treatment appointments over the next 12 months.

Secondary Objectives:

We will examine whether I-CBT has similar effects on related measures (pain sensitivity, anxiety sensitivity, distress tolerance, symptoms of specific phobia of dental procedures, blood-injury-injection phobia, sleep disturbance and sleep-related impairment, functional impairment due to dental anxiety, and consumer satisfaction) at one- and three-month follow-ups.

We will also examine whether the Internet-based intervention reduces anticipated and perceived pain and anxiety during dental procedures in immediately pursuant appointments for dental treatment.

We will also examine whether baseline levels of distress tolerance and pain sensitivity moderate the efficacy of the dental anxiety intervention.

5) Rationale and Significance

Page 2 of 28 Revision: May 12, 2023

Dental anxiety (i.e., anxiety related to undergoing dental procedures) is a major public health concern, as it leads to underutilization of dental care and poor oral health. Approximately 10-20% of individuals in the US endorse significant dental anxiety, and 10-50% cancel regular dental care appointments or delay treatment for a painful dental condition due to fears of dental procedures (Sohn & Ismail, 2005). Patients with dental anxiety are more likely to be referred for nitrous oxide sedation (Boyle, Newton, & Milgrom, 2009) and use emergency dental services (Kanegane, Penha, Borsatti, & Rocha, 2003), both of which increase individual and public dental healthcare costs. Dental anxiety has been consistently associated with increased oral health problems and impairment (e.g., more cavities; Armfield, Stewart, & Spencer, 2007). Few studies have examined the efficacy of psychological treatments for dental anxiety (Gordon, [name], Tellez, & Ismail, 2013), and most of the existing empirically supported psychological interventions cannot be easily disseminated within dental healthcare settings, as they must be administered by highly trained clinicians over a number of sessions. Therefore, it is the goal of our ongoing research program to develop a brief online therapy for dental anxiety that could be easily implemented in dental clinics, allowing for broader dissemination.

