We propose general statistical analyses and sample size considerations for the U01 trial. Initial analyses will be conducted to determine normality of distributions of the continuous variables, and any necessary transformations will be conducted. Primary outcomes will be the MDAS (score ranging from 5 to 25) and the rating of fear of dental procedures from the ADIS-5 (0=no fear to 8=very severe fear). All eligible patients will be randomly assigned to one of the three conditions described above. Although randomization should provide relatively comparable groups, demographic variables that differ between groups and are correlated with the primary outcomes will be used as covariates. Patients will receive a full battery assessment of outcome measures at baseline and 1 and 3 months after the day of their index dental appointment (as well as assessments on the day of their index dental appointment).

Page 16 of 28 Revision: May 12, 2023

Preliminary statistical analysis will include measures of central tendency and dispersion, as well as an examination of the bivariate relationships among the primary and secondary outcome variables (e.g., client satisfaction, blood-injury-injection phobia), potential moderators (e.g., distress tolerance and pain sensitivity), and demographic characteristics.

Differences between the groups on baseline demographic, clinical and psychological measures will be examined using χ^2 (Pearson) or Student's *t*-tests, as appropriate. Moreover, differences on the variables listed above among completers and drop-outs will also be explored. Both per protocol and intention to treat (ITT) analyses will then be conducted.

Specific Aim 1

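### The only randomised attendance comparison is an unadjusted chi-square, although Aim 3's before/after step already needs each I-CBT patient's prior-year attendance; the test is valid but less precise than it could be

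*Combined protocol and SAP*

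**What the plan says.** Section 4 introduces the objectives with "To achieve this overall goal, we propose 3 primary objectives", and the third reads "We will examine the impact that the intervention has on attendance at scheduled dental treatment appointments over the next 12 months". The opening of Planned Analyses in section 8(c) is narrower about outcomes: "Primary outcomes will be the MDAS (score ranging from 5 to 25) and the rating of fear of dental procedures from the ADIS-5". Attendance is therefore a primary objective but not a named primary outcome.

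Specific Aim 3 in section 8(c) has three steps:

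1. A one-sample chi-square on the overall attendance rate, "comparing the 12-month periods immediately before and immediately after the delivery of the intervention", with both I-CBT arms pooled.
2. The comparison between arms: "We will also use a Chi-square test to compare post-intervention attendance rates between the two intervention groups". The stated expectation is "We expect the attendance rates will be similar for the two groups".
3. A responder analysis: "Finally, we will conduct logistic regression analyses predicting attendance/nonattendance among intervention patients who did or did not demonstrate reduction in dental anxiety at 3-month follow-up". On covariates it adds: "Relevant demographic characteristics and other potential confounding variables or moderators will be included in the final logistic models".

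The section on attendance at dental appointments names the clinic's scheduling system as the data source. It says attendance will not be collected for active controls, who are offered the intervention after their 3-month follow-up. Under Missing Data, the ANCOVAs for Aims 1 and 2 control for baseline scores. Prior attendance is not named as a covariate anywhere.

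**The concern.** Because controls contribute no attendance data, step 2 is the only attendance comparison protected by randomisation. It uses post-intervention rates alone. The outcome's own baseline value, usually a useful predictor, is needed for step 1 but plays no part in step 2. The plan adjusts the same two-arm contrast for baseline in Aim 1 and gives no reason for doing otherwise here.

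What is at stake is the width of the interval around the difference between arms. The plan expects similar rates and sets no attendance margin. A non-significant chi-square cannot show similarity, so the confidence interval is what a reader will use to judge how large a difference remains possible.

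**Working it through.** **Is the baseline value available?** The prior-year window in step 1 is anchored to delivery of the intervention, which falls on a different date for each patient. The pooled rate therefore cannot be assembled without looking up each patient's own prior-year appointments. This is an inference from the window; the plan does not describe a patient-level extract.

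**Does another provision supply the adjustment?** The general covariate rule in Planned Analyses covers demographic variables that differ between groups and correlate with the primary outcomes, so it does not reach prior attendance. The logistic models in step 3 contrast patients with and without anxiety reduction, not arms.

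**Size.** The plan gives no attendance rate, effect size, power or pre/post correlation for Aim 3, so there is no figure of its own to reproduce. From the documents: about 550 patients over three roughly equal arms, 550/3 ≈ 183 per arm. Assumed: 75% attendance, two-sided 5% level, a range of correlations r, and a prior-year value for every patient.

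*One yes/no outcome per patient*

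- Unadjusted SE = √(2 × 0.75 × 0.25 / 183) = 0.0453; half-width = 1.96 × 0.0453 = 8.9 points.
- Adjusted SE = unadjusted SE × √(1 − r²).
- Power for an assumed 75% v 62%: SE = √((0.1875 + 0.2356)/183) = 0.0481; Φ(0.13/0.0481 − 1.96) = 77%.

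| r | √(1 − r²) | Half-width (points) | Power, 75% v 62% |
|---|---|---|---|
| 0 | 1.000 | 8.9 | 77% |
| 0.2 | 0.980 | 8.7 | 79% |
| 0.3 | 0.954 | 8.5 | 81% |
| 0.5 | 0.866 | 7.7 | 88% |

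A simulation with binary pre and post attendance (4,000 runs per setting, assumed rates of 70% and 80%) agrees. The ratio of adjusted to unadjusted variance was 1.00-1.01 at r = 0, 0.91-0.92 at 0.3 and 0.73-0.77 at 0.5. Type I error was 4.6-5.3% across both methods.

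*Proportion of bookings attended*

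Let attendance propensity vary between patients with mean 0.75 and SD σ (assumed), with m bookings in each period. The variance per patient is σ² + (0.1875 − σ²)/m, and r = σ² divided by that variance.

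| σ | m | Variance | r | Unadjusted half-width | Adjusted |
|---|---|---|---|---|---|
| 0.20 | 2 | 0.114 | 0.35 | 6.9 | 6.5 |
| 0.20 | 4 | 0.077 | 0.52 | 5.7 | 4.9 |
| 0.25 | 2 | 0.125 | 0.50 | 7.2 | 6.3 |
| 0.25 | 4 | 0.094 | 0.67 | 6.3 | 4.7 |

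On this scale, unadjusted power for a 13-point difference is already 94-99%. With m = 1 the same propensities give r of only 0.21-0.33 and a half-width of 8.7-8.4 points. The higher correlations thus belong with the narrower intervals and should not be combined with the 8.9-point figure.

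**The case against.** The strongest reply is that this is a refinement and not an error. The chi-square holds its type I error, the contrast is one of three Aim 3 analyses, attendance is not a named primary outcome, and without a margin no stated decision would change. All of that stands, and it limits the point to efficiency.

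The plan also speaks of an overall rate in a one-sample test, which could be run on totals, and the data-collection text describes only tracking after the intervention. That is fair on the wording. Even so, totals over patient-specific windows must be built from patient-level dates. Section 8(a) recruits anyone with a scheduled non-emergent appointment and requires no earlier visit, so some patients will have no baseline value. That stands too, and reduces the gain.

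A reader might infer more than the documents support:

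- *That prior attendance is discarded.* It is not; step 1 uses it.
- *That the responder analysis is biased because prior attendance is not named.* The covariate sentence for those models, "Relevant demographic characteristics and other potential confounding variables or moderators will be included in the final logistic models", already admits it as a potential confounder.
- *That adjustment is worth about a third more patients.* That needs r = 0.5 (1/(1 − 0.25) = 1.33). No document gives this value, and the propensities above do not reach it for a single yes/no outcome.

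**Conclusion.** The point holds as one of efficiency. The between-arm attendance test ignores a baseline value that Aim 3 itself requires, and nothing elsewhere in the plan supplies the adjustment. The test is not biased.

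For one yes/no outcome per patient, the half-width narrows by about 0.2 points at r = 0.2, 0.4 at r = 0.3 and 1.2 at r = 0.5, with nothing gained at r = 0. For the proportion of bookings attended, it narrows by roughly 0.4 to 1.6 points from an interval that is already tighter. Attendance rates, correlations, propensity spread and bookings per patient are all assumptions, and the plan does not say whether the unit is the patient or the appointment. The power figures use a 13-point difference that the plan does not expect, so interval width is the more relevant measure.

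**What to change.** In Specific Aim 3, state whether the attendance outcome is one value per patient or appointments attended out of those booked. Then make the between-arm analysis a logistic model or, for attended out of booked, a binomial model allowing for clustering by patient. Include arm, attendance in the prior 12 months and an indicator for no appointment in that period. Report the standardised (marginal) difference in attendance with its 95% CI, and keep the chi-square as supportive.

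The cost is a few lines of SAP text and code. The prior-year records are needed for the before/after step anyway, though they must be kept at patient level. The downside is that patients with no prior-year appointments contribute no baseline value and rely on the indicator, so the gain shrinks as their share grows. If prior attendance proves uninformative, the simulation shows essentially no loss from adjusting.
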